Week 2 (Visit 1a): Gestational Age 14-16 (Early GDM Dx) or 24-28 weeks (Regular GDM Dx)

RT-CGM and meter will be downloaded for intervention group and meter downloaded for the control group. Glucose logs will be collected. All participants will confirm they have completed RN gestational DM education and nutrition appointments per local standard of care. Vital signs, weight and medications and dose will be recorded at each visit and maternal ultrasound results if available (appendix M).

Week 6 (Visit 1b): Gestational Age 20-22 weeks (Early GDM Dx)

RT-CGM and meter will be downloaded for the intervention group and meter downloaded for the control group. Vital signs, weight and medications and dose will be recorded at each visit and maternal ultrasound results if available (appendix M).

Week 6/Week 14 (Visit 2): Gestational Age 30-32 weeks (Both Early GDM Dx and Regular GDM Dx)

RT-CGM and meter will be downloaded for the intervention group and meter downloaded for the control group. Vital signs, weight and medications and dose will be recorded at each visit and maternal ultrasound results if available (appendix M).

The control group will wear blinded CGM for 10 days and return during regularly scheduled OB visit. The study staff will follow up with participants to remind them to return the devices. If for any reason, the CGM device fails to capture at least 3 days of data, the participants may be asked to repeat this measurement at an unscheduled visit.

Week 10/Week 18 (Visit 3): Gestational Age 34-36 weeks (Both Early GDM Dx and Regular GDM Dx)

RT-CGM and meter will be downloaded for the intervention group and meter downloaded for the control group. Vital signs, weight and medications and dose will be recorded at each visit and maternal ultrasound results if available (appendix M).

Questionnaire on nutrition and exercise in pregnancy and satisfaction with CGM and lifestyle changes with CGM.

The control group will wear blinded CGM for 10 days and return during regularly scheduled OB visit. HgA1c and fructosamine will be collected.

The study staff will follow up with participants to remind them to return the devices. If for any reason, the CGM device fails to capture at least 3 days of data, the participants may be asked to repeat this measurement at an unscheduled visit.

Week 14 /Week 22 (Visit 4) Gestational Age 38- 40 weeks (Both Early GDM Dx and Regular GDM Dx)

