study visit 2 (with de-identified data) or it sends the information via wireless radio frequency to a monitoring/display device or to a cellular phone so one can see their own data on their glucose and we can download it remotely. The device automatically generates an alert for glucose < 55, and an alert will also be generated for glucose > 140 in the unblinded portion of the study. The intervention group participants will be given a handout (Appendix K) for troubleshooting these alerts, particularly during the blinded portion of the study. DEXCOM G6 is FDA approved for use in patients with diabetes and will be used in accordance with instructions as approved for diabetes. It is not currently approved for patients with gestational diabetes but will be used in accordance with instructions as approved for diabetes. The risk is minimal with use of this device. In this study, we recommend patients connect the CGM to their cell phones, but if unable/unwilling, we will provide transmitters for participants to allow for real-time monitoring. Study staff will insert the first sensor for the groups and demonstrate how to insert additional sensors for the intervention group who will continue to use RT-CGM. If this is to be done as a televisit, the sensors, transmitter, and device (if needed) will be mail to the participant. Then the study staff will walk the participant through the first insertion through a virtual zoom visit. Patients will also have a YouTube video available for reference for the patients. For the blinded control, the research coordinator will insert all sensors unless televisit is needed with procedure as above. The patients will be instructed on how to remove the sensor themselves after 10 days and bring back their scheduled OB visit. The intervention group will wear the RT-CGM continuously and change the sensor every 10 days for the duration of the pregnancy and have telephone support and may refer to the YouTube video on insertion if needed. The intervention participants will have RT-CGM download serially over the study during regularly scheduled OB visits or televisits. The control group participants will wear the blinded CGM at beginning, at 30-32 and 34-36 weeks of the study. If, during the blinded portion of the study, due to device malfunction (rather than subject non-compliance), the device records less than 3 days of data, the participant can return to restart another 10 days of blinded CGM data.

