Perception/Satisfaction with CGM and Fingersticks/Meter (Appendices J): The Harvard Joslin Diabetes Center has developed a series of questionnaires on CGM experiences, opinions and expectations that will be given at the end of the intervention and has been adapted for the GDM. Additionally, questions about food changes and activity changes that was created for CGM use(19,20) . Questionnaires have been adapted for use in those using only meter fingersticks and for GDM.

Sleep Questionnaire (appendix Q) The Pittsburgh Sleep Questionnaire is good tool for screening sleep disorders in the population and has been used in pregnancy (22,23)

N: Glucose/CGM Data /Evaluation Measures: The compliance and duration wear for participants with CGM will also be recorded. Glucose dynamics, e.g., average glucose, standard deviation, mean amplitude of glucose excursion (MAGE), time in range % (65 and 140 mg/dL), % high (>140 mg/dL), % low (<64 mg/dL), and severe low % (<54mg/dL) and coefficient of variation (CV) and other statistical measures of glucose variability in those with CGM will be reviewed from the RT- CGM device data at baseline and visit 2-4. Blinded CGM values will be obtained at baseline and visit 2 and 3.

Glucose meter: Compliance with fingersticks 4 times a day will be recorded by average number of fingersticks per day. Glucose data including: average glucose, standard deviation, mean amplitude of glucose excursion (MAGE), time in range % (65 and 140 mg/dL), % high (>140 mg/dL), % low (<64mg/dL), and severe low % (<54mg/dL) will also be recorded.

N:Antenatal Ultrasound Markers: estimated fetal weight (in grams and percentile) using Hadlock scale, Biparietal Diameter, Head circumference, abdominal circumference, and femur length. Amniotic Fluid Index.

O: Delivery Outcomes:

Obstetric Outcomes:

- 1.Gestational age at delivery
- 2.Labor status (spontaneous labor, induced labor, no labor). For induced labor include indication for induction
- 3.Mode of delivery (vaginal delivery, cesarean delivery, operative vaginal delivery) including indication for delivery
- 4.Shoulder dystocia: defined as a delivery that requires additional obstetric maneuvers to release the shoulders after gentle downward traction has failed. SD occurs when either the anterior or, less commonly, the posterior fetal shoulder impacts on the maternal symphysis or sacral promontory

Maternal Outcome:

1. Preeclampsia or GHTN
2. Maternal insulin or medication use

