When the subject enrolls in the study, she will be assigned a unique study number that is not any part of her social security number or other personal identifier. These unique study numbers will be used to identify all information that subjects provide and any information that is collected from their medical records. The unique study numbers will be assigned sequentially according to the order of study enrollment and subjects will be identified by the initials of the group to which they are randomized and 3 numbers according to their entry into the study beginning with 001. Therefore, the first subject randomized to the DMC (control) group will be DMC-001 and the first subject randomized to the DMCGM (intervention) group will be DMCGM-001. A total of 50 DMC and 50 DMCGM subjects will be enrolled.

Although every precaution is being taken to protect participant privacy, breach of confidentiality is always possible. In the unlikely event of a breach of confidentiality, the nature of the research data is not of a sufficiently personal nature to negatively affect employment status, lead to civil/criminal liability, incur financial risks to the study participants, or other risks.

T. Subject Compensation:

Participants will be given \$50 after visit 0 and \$50 after visit 3. Visit 3 compensation will be given to participant upon return of blinded device or RT-CGM download at 34-36 weeks. If lack of CGM data necessitates unscheduled visits, the participant will receive an additional \$25 per visit up to a maximum of \$50 if 2 unscheduled visits are required. Subjects will also have use of the medical devices during the study for free: in the intervention group they will receive a glucose meter and test strips (total 50 test strips for free) to be used as needed. In the control group they will receive a glucose meter and 400 test strips for free if not covered by their insurance. No additional cost will be incurred by subjects.

If extra visits are necessary we will follow the OB clinic guidelines for COVID 19 screening. This money can be used for travel and parking but all study visits are piggy backed to a regular clinic visit so no extra travel or parking is required by the study although visits may be a little longer than usual

U. Appendix:

- A. Educational Material: Real-Time Continuous Glucose Monitoring educational material (A1) or Fingerstick educational material (A2)
- B. Table of Study Measurements
- C. Pre-Screening Checklist Telephone

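### The plan does not define which RT-CGM days form the Visit 2 and 3 values; the visit procedures point to earlier days than the control wear, and the RT-CGM baseline is already on treatment

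*Combined protocol and SAP*

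**What the plan says.** The time points for CGM evaluation are in Section N (Glucose/CGM Data/Evaluation Measures): "RT- CGM device data at baseline and visit 2-4. Blinded CGM values will be obtained at baseline and visit 2 and 3". No days are attached to these labels. Section E (Data Analysis Plan) applies mixed models to the CGM and variability measures at time points it calls key, without defining them.

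The data arise differently in the two arms. In Section H, at Visits 2 and 3, "RT-CGM and meter will be downloaded for the intervention group and meter downloaded for the control group". For the same visits, "The control group will wear blinded CGM for 10 days and return during regularly scheduled OB visit". Section J (Medical Devices) adds that "The intervention group will wear the RT-CGM continuously and change the sensor every 10 days for the duration of the pregnancy". It has the research coordinator insert the control sensors, in person or guided by televisit, and for removal: "The patients will be instructed on how to remove the sensor themselves after 10 days and bring back their scheduled OB visit".

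If a control sensor "fails to capture at least 3 days of data, the participants may be asked to repeat this measurement at an unscheduled visit". This is a trigger for repeat wear, not a rule for what enters the analysis.

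At week 0, Section H has controls start blinded wear and the intervention arm start RT-CGM with its readings visible. Section N still lists a baseline for both arms.

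**The concern.** A download at a visit can hold only readings up to that visit. A sensor placed at a visit and worn for 10 days holds readings after it. An analyst who takes each arm's data as the visit procedures deliver them would compare RT-CGM days before the visit with control days after it. Section T encourages this pairing: "Visit 3 compensation will be given to participant upon return of blinded device or RT-CGM download at 34-36 weeks".

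The offset goes with the arm, so randomization does not remove it. Any trend in glucose with gestation, or with time on treatment, would enter the between-arm comparison of the Aim 1 CGM metrics. Visits 2 and 3 are the only time points after week 0 at which both arms are scheduled for CGM evaluation, so the choice affects all of the later contrast. Even without bias, an unstated window leaves several versions of the same outcome open.

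Record length may also differ. For mean glucose and percentage in range this mainly affects precision. SD and CV over a longer record also take in slow drift.

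The baseline raises a related problem. If visible readings change behavior within days, a change-from-baseline or group-by-time test treats part of the early treatment effect as the starting value.

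**Working it through.** The plan gives no figure to reproduce, so the check is a count of days with the visit as day 0.

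**Inputs**
- Control wear: 10 days (Sections H and J), taken as days 0 to 9. That it starts at the visit is inferred from coordinator insertion, 10-day wear and later return; no sentence says so outright.
- RT-CGM download at the visit (Section H): days −L to −1, where L is the look-back. The plan does not give L.
- Spacing of Visits 2 and 3: Section H puts Visit 2 at study week 6 or 14 and has "Week 10/Week 18 (Visit 3): Gestational Age 34-36 weeks", so nominally 4 weeks, or 28 days. The Figure 2 footnote sets a minimum of 2 weeks, or 14 days. The Figure 2 bands (30-32 and 34-36 weeks) allow 30w0d to 36w0d, or 42 days.

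**Formula:** gap between midpoints = L/2 + 10/2.

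| Look-back L (days) | Basis | Gap (days) | Control days shared |
|---|---|---|---|
| 10 | assumed, same length as control wear | 5 + 5 = 10 | 0 of 10 |
| 14 | minimum spacing | 7 + 5 = 12 | 0 of 10 |
| 28 | nominal spacing | 14 + 5 = 19 | 0 of 10 |
| 42 | Figure 2 bands | 21 + 5 = 26 | 0 of 10 |

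RT-CGM is the earlier window in every row. If the visit day counts in both windows, the 10-day case shares 1 day and the gap is 9. Example: for a Visit 3 at 34w0d and a 10-day look-back, RT-CGM covers 32w4d to 33w6d and control wear covers 34w0d to 35w2d.

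The 14-, 28- and 42-day rows apply to Visit 3. No since-last-visit figure is given for Visit 2, because Section H and Figure 2 place the preceding visit differently for women diagnosed early.

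**Other readings of the visit value**
- All RT-CGM days in the 30w0d to 32w0d band: midpoint 31w0d, day 217. A control visit at 30w0d (day 210) has midpoint 210 + 5 = 215, which is 2 days earlier, with 10 days shared. A visit at 32w0d (day 224) has midpoint 229, which is 12 days later, with none shared. The 34-36 week band gives the same result.
- RT-CGM days 0 to 9 from the visit: gap 0, with 10 of 10 shared.

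**Gestational-age scale.** Assume visits are uniform over a 2-week band, with a 10-day look-back. A control and an RT-CGM participant share some days when the control's visit is the earlier one, which has probability 0.50. The mean overlap across all pairs is 2.2 days. The mean gap is still 10 days.

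**Baseline.** Both arms start wear at week 0, so timing is close: about 14 days of RT-CGM by week 2 against 10 control days gives midpoints 14/2 − 10/2 = 2 days apart. What differs is exposure: the RT-CGM record is unblinded from its first day.

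**The case against.** The plan never says that the analyzed value is the pre-visit download. Downloading is a transfer step, and Section J allows app data to be read remotely and reviewed later. The sentence in Section T triggers a payment and does not define data. If the control device is returned at 34-36 weeks, both arms could look back from that contact, as Section H arranges at week 2. Appendix B, the table of study measurements, is cited but is not in the public text and may settle the question. The trial is described as a pilot, and the mixed models can take gestational age as a covariate.

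Much of this stands. The offset is conditional on the download reading, the start of control wear is an inference, and Section T cannot establish a window. It does not remove the gap: Sections E and N leave the days undefined, and the procedures for Visits 2 and 3 lead most directly to the mismatched version. Section E permits covariates but does not name gestational age.

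A reader might infer that the arms' CGM records never overlap. The documents do not support that. Zero shared days holds only relative to each woman's own visit and only if downloads are used; by gestational age, windows of different women can overlap.

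**Conclusion.** The RT-CGM days behind the Visit 2 and Visit 3 values are undefined in Sections E and N. If visit downloads are used, and control wear starts at the visit, the RT-CGM window is systematically earlier: by 10 days with a 10-day look-back, 19 at nominal spacing, and up to 26 at Visit 3 within the Figure 2 bands. Record lengths would be 10 or more days against 10. The average offset remains on the gestational-age scale.

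Separately, and without needing the download reading, the RT-CGM baseline is an on-treatment record.

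A reader might go further and infer that the CGM comparison is biased toward one arm, or that the sample-size outcome is compromised. Neither follows. The documents give no trend from which to derive a size or direction in mg/dL, and HbA1c, on which the sample size rests, does not depend on these windows. The matching RT-CGM days should already exist because wear is continuous, so this should be settled in the plan before analysis and calls for no new design.

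**What to change.** State the following in Sections E and N for the between-arm CGM metrics:

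- **Windows at Visits 2 and 3.** Controls: the actual blinded wear dates. RT-CGM: the 10 days starting at the corresponding visit, cut from the continuous record.
- **Gestational age.** Include actual gestational age at the window midpoint in the mixed model. This also handles repeat wears at unscheduled visits, which cannot be matched by visit.
- **Minimum data.** Apply one stated rule to both arms. Using the 3-day repeat-wear trigger for this would be a new choice and should be declared as one.
- **Week 0.** Do not use this CGM record as a pre-treatment baseline in change or group-by-time tests. Compare the arms on it as an early on-treatment window, using the first 10 days in each.
- **Visit 4.** Report RT-CGM descriptively, since no control CGM is planned then.

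If Appendix B already defines the windows, a cross-reference in Section N may cover the first item.

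The cost is wording and a date filter. Days after Visit 2 are in the Visit 3 download; days after Visit 3 come from the Visit 4 or remote download. Only receiver-only women who do not reach Visit 4 need one more download. The downside is that some RT-CGM days drop out of the between-arm test; they remain available for the exploratory trajectory graphs in Section E.

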pregnancy obstetric provider. The intervention group will continue the RT-CGM device and will be instructed to continue fingersticks only when concerned for hypoglycemia and/or inaccuracy of sensor. The control and intervention groups will follow-up serially for the duration of pregnancy (see schematic for visits below). The control group will wear the blinded CGM at serial timepoints throughout pregnancy and the intervention group will have serial download of RT-CGM. Participants will also have labs checked every 8 weeks which will include HbA1C and fructosamine at beginning and end of the study. It is estimated that participants will be enrolled at 24-28 weeks and have 4 visits (estimating a pregnancy duration of 40 weeks). Some participants may receive a diagnosis of gestational diabetes earlier and thus have more sessions. Maternal and neonatal outcomes will be abstracted from delivery records.

[figure not shown]

Figure 1: Study Design Schematic: N=100 Control N=50 GDM Intevention: GDM N=50

*Approximate Total duration of CGM use would be 14-22

**see timeline for measures appendix B

Figure 2: Timeline for Visits Based on High Risk for Gestational Diabetes and Typical Risk

		Screening Visit 0	Visit 1b High risk	Visit 1a	Visit 2++	Visit 3	Visit 4*
Gestational age Intervention	High Risk	14	20-22 weeks	24-30 weeks	30-32 weeks	34-36 weeks	38-40 Weeks

Gestational age Intervention	Typical Risk	24-28	N/A	24-30 weeks	30-32 weeks	34-36	38-40 Weeks
Gestational age Control	High Risk	14	14-16 weeks	24-30 weeks	30-32	34-36	38-40 Weeks
Gestational age Control	Typical Risk	24-28	N/A	24-30 weeks	30-32 weeks	34-36	38-40 weeks

+++ visits will be a minimum of 2 weeks apart

*38-40 week data only collected in participants that make it to 38- 40 week gestational age

Screening/Pre-Intervention Visit(week 0):

Consent (appendix R) will be obtained prior to any screening procedures being completed, and conducted in a quiet room or private televisit. Participant will be given ample time to ask questions, and a copy of the signed consent form will be given prior to start of screening visit. Participants will fill out a contact form, including emergency contact. Study staff will review medical history and medications, pregnancy history, patient's mother's pregnancy history, sleep history, and lipid profile if available (appendix D), as well as all inclusion/exclusion criteria.

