The receiver and/or the app will display the glucose reading along with a rate of change arrow and a trend graph. Additionally, the receiver and/or app issues alarms and alerts to notify the patient of glucose level changes and other important system conditions. The app provides the additional capability to share data with “followers” using the Dexcom Share service. The receiver can be put into a blinded mode using CLARITY® software. In this mode, users are unable to see the CGM data or receive CGM alerts.

CGM Ancillary Devices Dexcom CLARITY® is an accessory for users of the Dexcom CGM system. It is a software program that allows the transfer of glucose data from the CGM system to Dexcom remote servers for data management to allow the use of the CGM data by the user and study clinicians. Target ranges of 65 to 140 mg/dl [3.6 to 7.8 mmol/l] will be set and the patients will be introduced to the use of alarm settings. Both participants and study sites will use CLARITY® to transfer glucose data between user and study site, whether CGM is used in blinded or real-time mode. A CLARITY® mobile app can be used for a retrospective review of glucose data on the smart device and can also be set up to allow receipt of push notifications of CGM data facilitating data review. For all patients (intervention and control group) an anonymized CLARITY® account will be created by using a sequential study number which is allocated at randomization.

Intervention Group:

- For participants who have a supported phone, the DEXCOM G6 CGM app will be installed on participant's smart phone.
- An anonymized CLARITY® mobile account will be set up and linked to the research site.
- Participants will use CGM data to log their blood sugars for fasting and 1-hour post-meals for review by their OB provider. The OB providers will not specifically use the CGM in their management decisions.
- A high alert threshold will be set at 140 mg/dl [7.8 mmol/l]. Low alert threshold and urgent low soon alerts will be turned off. If participants require insulin, the low alert will be turned on and the threshold set at 65 mg/dl [3.6 mmol/l]. In addition, the urgent low alert (55 mg/dl [3.1 mmol/l]), the urgent low soon alert (when glucose levels

are falling fast and will be below 55 mg/dl [3.1 mmol/l] in less than 20 min) as well as alerts for rise and fall rate (3 mg/dl [0.17 mmol/l]) in addition to alerts for signal loss and no readings for more than 20 min will be enabled.

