- Participants with applicable smart phones may have CLARITY® push notifications on the CLARITY® mobile app about weekly time in range comparison enabled during the study.

- For app users, the “Share and Follow” functionality will be discussed and encouraged (i.e. the study participants are able to invite followers to review their glucose levels).

- For participants using the receiver only, the receiver will be downloaded into the CLARITY® clinic account at each visit. CGM data and reports. RT CGM-Participants will also keep a logbook of their blood sugars for their provider to review.

Control Group

The participants of the control group will perform self-monitored blood glucose testing with a study-provided blood glucose meter, including testing supplies. They will perform capillary blood glucose monitoring as routinely used for patients with GDM, i.e., at least four capillary blood glucose values daily including measurements in a fasting state as well as 1h after starting each meal. The study participants will keep a logbook of their glucose values

Each participant of the control group will be assigned a study blood glucose meter to measure and store their blood glucose values during the study.. A commercially available desktop software used in conjunction with the glucose meter for blood glucose monitoring will be utilized for downloading the meter data at each visit ensuring that dates and times are correct. Blood glucose meters used by the control group will be assessed to establish frequency of testing (overall and per week) as well as percentage of days with less than four measurements per day.

Subjects who got randomized to the control group then decided to withdraw from the study and discontinue their participating in the study will receive an email asking them to fill out a survey questionnaire to explain the main reason and any other reasons for withdrawal from the study. The survey will be sent to subjects’ email through a link from Redcap and it won’t take more than 10 minutes to complete.

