3. Maternal hypoglycemia: symptoms or asymptomatic biochemical hypoglycemia (fingerstick or RT-CGM less than 54 mg/dL (3.0 mmol/L), severe (fingerstick or RT-CGM < 64mg/dl (3.6 mmol/l)
4. Maternal weight gain

Fetal Outcome:

1. Gestational age at delivery
2. Live born or stillbirth

3. Birth weight: (large for gestational age, small for gestational age, macrosomia, birthweight ratio). Large for gestational age: birthweight > 90th centile for gestation using Fenton 2013 growth charts. Small for gestational age: birthweight below the 10th centile using Fenton 2013 growth charts. Macrosomia: birthweight ≥ 4 kg.
4. Birthweight ratio (birthweight adjusted for gestation and gender calculated with the Fenton 2013 web calculator (<http://peditools.org/fenton2013>)).
5. 5- minute Apgar score
6. Respiratory distress
7. Neonatal hypoglycemia: defined as < 4 h of life: < 1.4 mmol/l (30 min after first feed); < 2.2 mmol/l (1 h after subsequent feeds), 4–24 h of life: < 1.9 mmol/l (prefeed); < 2.5 mmol/l (1 h after feed)
8. NICU admission including LOS
9. Birth injury (such as brachial plexus injury)
10. Hypoxic ischemic encephalopathy

P. Risks and Side Effects:

There are various possible risks and side effects that a participant may incur as a result of this study. At the beginning of the study, when participants are administered the informed consent form by research staff, they will be informed that their participation is completely voluntary and will be informed of the risks and benefits. They are free to leave the study at any time and will not be penalized. Potential subjects will also be told that failure to participate in no way affects the usual care they would receive from their OB provider. Only after all questions have been answered, both study staff and the participant will sign and date the consent form.

It is very unlikely that there will be any adverse events

There are possible risks associated with the intervention activities, including the medical device, including:

- a. Less Likely (1% \leq Event Rate < 5%): CGM site infection or tape allergy (<1-2%) (41)
- b. Likely (5% \leq Event Rate < 10%): None
- c. More likely (Event Rate $\geq 10\%$): None

Risk to Participants:

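### Maternal hypoglycaemia is ascertained by fingerstick or RT-CGM, without the controls' blinded CGM, so asymptomatic lows are far more likely to be found in the RT-CGM arm

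*Combined protocol and SAP*

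**What the plan says.** **Outcome definition.** Section O, Maternal Outcome item 3, counts symptoms or "asymptomatic biochemical hypoglycemia (fingerstick or RT-CGM less than 54 mg/dL (3.0 mmol/L". The same two sources, fingerstick or RT-CGM, are repeated for the severe category. Blinded CGM is not mentioned. Section N treats RT-CGM device data and blinded CGM values as separate things, so the omission cannot be read as mere shorthand.

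**Control arm.** Section J asks for "at least four capillary blood glucose values daily including measurements in a fasting state as well as 1h after starting each meal". Section C remarks that fingerstick data are not usually available overnight. For CGM, Section J says: "The control group participants will wear the blinded CGM at beginning, at 30-32 and 34-36 weeks of the study". Each wear lasts 10 days. Section N agrees: "Blinded CGM values will be obtained at baseline and visit 2 and 3".

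**RT-CGM arm.** Section J: "The intervention group will wear the RT-CGM continuously and change the sensor every 10 days for the duration of the pregnancy". Section H tells these participants to log any reading under 60 mg/dL that they see on CGM, and to "continue fingersticks only when concerned for hypoglycemia and/or inaccuracy of sensor".

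**Other glucose measures.** For the meter, Section N lists "Glucose data including: average glucose, standard deviation, mean amplitude of glucose excursion (MAGE), time in range % (65 and 140 mg/dL" and further low and high percentages, as items also recorded. Section E (Data Analysis Plan) derives each participant's glycaemic variability from the CGM data and puts CGM readings and variability into the mixed models. It does not mention meter values.

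**The concern.** The chance that an asymptomatic low is counted depends on how often glucose is looked at. Under the Section O definition that differs by arm:

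- Controls are observed at about four fixed daytime points, three of them an hour after a meal and none overnight.
- RT-CGM users are observed day and night. Their fingersticks are also taken when a low is suspected, so their meter record is enriched for lows.

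Both differences push in the same direction. With identical true risk, the RT-CGM arm would appear to have more hypoglycaemia. If RT-CGM truly reduces lows, as Aim 6 supposes for the night, the detection difference would hide some or all of that benefit. The comparison of this maternal outcome under Aim 2 would then partly measure surveillance rather than glucose.

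**Working it through.** The plan gives no figure for detection, so there is none to reproduce. Two checks follow.

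**Check 1: detection under the definition as written**

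Inputs:
- Four fingersticks a day in controls (Section J, which states a minimum of four).
- Continuous wear in the RT-CGM arm (Section J).
- Assumptions, not in the documents: asymptomatic episodes of d = 15, 30 or 60 minutes; random timing over 24 hours, independent of the fingersticks; equal true risk in both arms; a working sensor that reads at least once per episode.

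Chance that one episode is hit by a fingerstick: p = 4d/1440.

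- d = 15: 60/1440 = 0.042
- d = 30: 120/1440 = 0.083
- d = 60: 240/1440 = 0.167

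Chance that a control with n episodes is flagged at least once: 1 − (1 − p)^n.

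| Episodes per woman | 15 min | 30 min | 60 min | RT-CGM arm |
|---|---|---|---|---|
| 1 | 4% | 8% | 17% | nearly 100% |
| 3 | 12% | 23% | 42% | nearly 100% |
| 10 | 35% | 58% | 84% | nearly 100% |

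The gap narrows as episodes become longer or more frequent, but it never changes direction. Random timing probably flatters the meter: overnight episodes would mostly be missed, and three of the four scheduled readings follow a meal.

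**Check 2: would adding blinded CGM to the definition be enough?**

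Inputs:
- Controls: 3 wears × 10 days = 30 CGM days (Sections J and N).
- RT-CGM arm: Figure 1 gives a total CGM duration of 14-22 with no unit. Read as weeks, in line with the visit headings, this is 14 × 7 = 98 to 22 × 7 = 154 days.

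Ratio of observation time: 98/30 = 3.3 to 154/30 = 5.1.

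If three randomly timed episodes are spread over the whole period, the chance that at least one falls in a blinded wear is:

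- 98 days: 1 − (1 − 30/98)^3 = 0.67
- 154 days: 1 − (1 − 30/154)^3 = 0.48

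Nearly all RT-CGM users would again be flagged. Naming blinded CGM therefore helps but does not equalise detection. The windows must also match, and visit 4 has no control CGM at all (Section N).

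**Threshold labels side by side**

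- Section N: the severe low percentage is below 54 mg/dL, and the ordinary low percentage is below 64 mg/dL.
- Section O: the ordinary category is below 54 mg/dL, and the severe category is below 64 mg/dL.

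The two sections contradict each other and must be reconciled before any hypoglycaemia comparison can be defined.

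**The case against.** **Controls do have CGM.** They wear it blinded for 10 days on three occasions. Section J routes both arms' data through the same software, "whether CGM is used in blinded or real-time mode", and Section N lists CGM percentages below 64 and below 54 mg/dL. A like-for-like comparison of low glucose is therefore available. This stands, and it is why the fix is cheap. It does not repair item 3 of Section O, which names other sources.

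**A tempting stronger reading.** A reader might infer from the meter list in Section N that time in range and MAGE cannot be compared between arms because they come from different devices. The documents do not support this. Section E takes variability from CGM data, controls have CGM at three time points, and no section assigns meter values to a between-arm test. What remains is that no section excludes meter values or limits RT-CGM to the controls' windows.

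**A large reading-rate ratio.** A reader might also size the problem by readings per day. The documents give no sensor sampling interval. Intervals of 1 to 15 minutes would give ratios from 360 down to 24 against four fingersticks. Nor is the outcome defined as a count of readings, so such a ratio is not the bias in a per-woman outcome.

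**No stated test, and symptoms count in both arms.** The plan attaches no hypothesis test to item 3, sizes the study on HbA1c (Section E) and calls itself a pilot (Section B). Symptomatic events can be ascertained in either arm. This limits the point to asymptomatic lows. It also means one cannot say that a safety conclusion would be reversed, since the observed difference also depends on any true effect of RT-CGM.

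**Conclusion.** The ascertainment rule for maternal hypoglycaemia is wrong as written. It detects asymptomatic lows unequally by arm and biases the comparison towards more events with RT-CGM. In the illustration with three episodes per woman, about 12% to 42% of controls would be flagged against nearly all RT-CGM users. Those percentages rest on assumed episode number, length and timing. The direction rests only on the documents' monitoring schedules. Adding blinded CGM without matched windows would leave a 3.3- to 5.1-fold difference in observation time, if 14-22 means weeks.

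For time in range, time below range, MAGE and CV, the plan needs clarification, not correction. The contradictory severe thresholds are a separate defect in the same text.

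**What to change.** 1. For the between-arm comparison, define biochemical hypoglycaemia from CGM in both arms over the same three 10-day windows: study start, 30-32 weeks and 34-36 weeks, blinded in controls. Express it relative to valid wear time, and apply one minimum-wear rule to both arms.
2. Report symptomatic and fingerstick-detected events separately, as description by arm.
3. State in Section E that between-arm time in range, time below range, MAGE and CV come from CGM in those same windows. Keep meter values for describing testing adherence and readings in target.
4. Reconcile the severe thresholds in Sections N and O.
5. Note that RT-CGM users see their readings from week 0 (Section H), so the first window is not a pre-treatment baseline in that arm.

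The cost is a change of wording in Sections E, N and O, with no new data collection. The downside is that hypoglycaemia outside the windows, including everything at visit 4, is described but not compared.
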